### 4.2. Randomization, Stratification, and Blinding

Subjects who meet all of the inclusion criteria and none of the exclusion criteria will be assigned a subject randomization number via an Interactive Web Response System (IWRS) on Day 1 after a wash-out/prophylaxis period (from Visit 2 to Visit 3) that will follow screening (Visit 1).

The randomization will be stratified by post-washout/pre-dose sUA (<9.8 mg/dL or  $\geq 9.8$  mg/dL) at Visit 3 and by the presence or absence of tophi at screening (Visit 1).

If a subject has experienced a gout flare during the wash-out/prophylaxis period, the subject will not be randomized and can be rescreened once 3 weeks after resolution of gout flare.

If a subject cannot be randomized, the reason will be recorded in the screening disposition page. The IWRS must be notified immediately that the subject was not randomized.

Before unblinding, all individuals involved in this study remain blinded unless the nature of their activities in the study specifically requires them to be unblinded, and surrogate or dummy groups will be applied to statistical analysis.

Client authorization documented via Biostatistics Unblinding Request/Authorization Form should be obtained prior to receipt/transfer of data and/or access is granted to unblinded information.

### 4.3. Reporting Conventions

- Data from all study centers will be combined for analysis;
- Confidence intervals (CIs) will be presented as 2-sided 95% CIs unless specified differently in specific analysis;
- Summary statistics will consist of the number and percentage of subjects in each category for discrete variables, and the number of subjects (or events, if appropriate), mean,

median, standard deviation (SD), minimum, Q1, Q3, and maximum for continuous variables;

- All mean and median values will be formatted to one more decimal place than the measured value. Standard deviation values will be formatted to two more decimal places than the measured value. Minimum and maximum values will be presented to the same number of decimal places as the measured value.
- P-values will be rounded to 4 decimal places. P-values that round to 0.0000 will be presented as ‘<0.0001’ and p-values that round to 1.000 will be presented as ‘>0.9999’.
- All percentages will be rounded to one decimal. The number and percentage of responses will be presented in the form XX (XX.X%), where the percentage is in the parentheses;
- All laboratory data will be reported using international system of units (SI);
- All listings will be sorted for presentation in order of dose cohort, study center, subject ID, and date of procedure or event;
- All analysis and summary tables will have the analysis population sample size for each dose cohort in the column headers in form of N=XXX;
- The day of the first dose of study treatment will be defined as Day 1;
- Baseline value will be defined as the last non-missing value from the evaluation on or before the first dose of study drug is administered. In case of re-evaluation, value from the last test will be used as the baseline.

#### **4.4. Analysis Sets**

##### **4.4.1. All Randomized Set**

The All Randomized Set includes all randomized subjects who are assigned subject randomization numbers.

The All Randomized Set will be applied to summaries of subject disposition, based on treatment that subjects were randomized.

##### **4.4.2. Safety Set**

The Safety Set includes all subjects who received any study medication (LC350189, febuxostat, or placebo). The Safety Set will be applied to demographics and baseline characteristics, and safety analysis, based on treatment that subjects received.

##### **4.4.3. Full Analysis Set**

The Full Analysis Set (FAS) is defined as all randomized subjects that received at least one dose of investigational products (LC350189, febuxostat, or placebo).

The FAS will be applied as the primary population for efficacy analysis, based on treatment that subjects were randomized.

##### **4.4.4. Per-Protocol Analysis Set**

The Per-Protocol Analysis Set (PPS) is defined as all subjects in the FAS that are compliant with treatment and have appropriate exposure to study medication for the 12-week treatment period and without any major protocol deviations that may impact primary efficacy analysis.

Major protocol deviations that may impact the primary efficacy analysis, rules for handling subjects who ever took unassigned dose or type of study treatment, algorithm for calculating overall study treatment compliance, and cutoff treatment compliance values for PPS exclusion will be determined during a blinded data review meeting (DRM) prior to DBL. If a subject withdrew from the study prematurely without Week 12 data to assess the primary and/or key secondary endpoints, he or she may be excluded from the PPS. If a subject completed the treatment period and had sUA result within 84 days +/- 5 days, he or she will be included in the PPS.

For subjects who ever received unassigned dose of study treatment but stayed in the same dose for the entire study treatment, the subject can be included in the PPS if subject received one of the pre-defined dose in the study (LC350189 50 mg, 100 mg, 200 mg, or placebo).

The PPS will be used for supportive analyses of the efficacy endpoints, based on treatment that subjects received.

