### 7.2.2. Study Drug Compliance

Based on treatment group, study drug compliance will be measured at specific visits using the following formula:

| Treatment Group | Study Drug       |                  | Compliance (D) |
|-----------------|------------------|------------------|----------------|
|                 | Bottle 1         | Bottle 2         |                |
| LC350189 50 mg  | LC350189 25 mg   | LC350189 25 mg   | (B/2)/C*100%   |
| LC350189 100 mg | LC350189 100 mg  | LC350189 Placebo | B/C*100%       |
| LC350189 200 mg | LC350189 100 mg  | LC350189 100 mg  | (B/2)/C*100%   |
| Placebo         | LC350189 Placebo | LC350189 Placebo | (B/2)/C*100%   |

Where B is the total number of dispensed non-placebo capsules minus the total number of returned non-placebo capsules including lost or damaged ones (for Placebo group, placebo capsules of LC350189 will be considered), and C is the number of days since Day 1 for Day 28 (Visit 6); the number of days since Day 28 for Day 56 (Visit 7), and the number of days since Day 56 for Day 84 (Visit 8).

| Period             | Day when Accountability is Measured | Day when Bottles were Dispensed | B   | C (days)  |
|--------------------|-------------------------------------|---------------------------------|---|---|
| Visit 4 to Visit 6 | Day 28                              | Day 1                           | Sum of (35 minus the number of capsules left in each of bottle including lost or damaged ones)                              | (Date of Visit 6 – Date of First Dose of Study Treatment)   |
| Visit 6 to Visit 7 | Day 56                              | Day 28                          |   | (Date of Visit 7 – Date of Visit 6)   |
| Visit 7 to Visit 8 | Day 84                              | Day 56                          |   | (Date of Visit 8 – Date of Visit 7) *   |
| Overall            | Day of Last Dose                    | Day 1                           | Sum of (all dispensed non-placebo capsules) minus Sum of (all returned non-placebo capsules including lost or damaged ones) | (Date of Visit 8 – Date of First Dose of Study Treatment)
For early terminated subjects: (End of Treatment Date – Date of First Dose of Study Treatment + 1) |

\* Subjects will be guided not to administrate the study drug on Day 84. Even if the drug is administrated, it will be administrated after assessments. Therefore, Day 84 is exclusive to derivation of study drug compliance.

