#### 7.2.4. Subjects Who Ever Took Unassigned Dose

In practice, a subject may receive and take LC350189 capsules with unassigned doses therefore actual dosage may be different from pre-defined study doses (LC350189 50 mg, 100 mg, or 200 mg). In that case, subjects will be summarized in the most frequently applied dose level and the “LC350189 All” column in Safety tables. If the most frequently applied dose level is not in the pre-defined doses, the subject will be summarized only in the “LC350189 All” column.

Examples: Assuming a subject was assigned to 50 mg group. 1) If this subject took proper doses during the majority of the treatment period and a few 200 mg doses by chance, this subject will be categorized in 50 mg group; 2) If this subject took 200 mg doses during the majority of the treatment period and a few 50 mg doses, this subject will be categorized in 200 mg group; 3) If

for some reasons this subject took 150 mg doses for the entire treatment period, this subject will be not categorized into any pre-defined doses, and summarized only in the “LC350189 All” column.

In Safety Analysis, 1) subjects in Febuxostat group took both active Febuxostat and its placebo will be summarized in “Febuxostat” column, 2) subjects in Placebo group took both active Febuxostat and its placebo will be summarized in “Febuxostat” column, 3) subjects in Febuxostat group took only Febuxostat placebo will be summarized in “Placebo” column, and 4) subjects who took both active Febuxostat and active LC(50mg, 100mg, or 200mg) dose will be summarized in the most frequently applied dose group..

Subjects who ever took unassigned dose will be excluded from PPS, unless the unassigned doses taken were administered for the entire treatment duration.

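### The SAP's compliance formula depends on the treatment arm and contradicts itself, yet the compliance rules for the Per-Protocol Set are to be settled at a blinded meeting

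*SAP*

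**What the plan says.** SAP 4.4.4 requires PPS subjects to be compliant with treatment and hands the detail to a meeting held under the blind: "cutoff treatment compliance values for PPS exclusion will be determined during a blinded data review meeting (DRM) prior to DBL". The algorithm for overall compliance, the major deviations and the rules for unassigned doses go to the same meeting. The section also says that subjects who complete treatment and have a serum uric acid result at Day 84 ± 5 days will be included, and attaches no compliance condition to that sentence.

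SAP 7.2.2 nevertheless gives a compliance algorithm. The 100 mg arm, whose second bottle is placebo, uses B/C. The 50 mg, 200 mg and placebo arms use (B/2)/C. Before protocol version 5.0, febuxostat also uses B/C. The numerator is defined by arm: "Where B is the total number of dispensed non-placebo capsules minus the total number of returned non-placebo capsules including lost or damaged ones", with LC350189 placebo capsules counted instead in the placebo arm.

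Under SAP 4.2, until unblinding, "surrogate or dummy groups will be applied to statistical analysis", and access to unblinded information needs documented authorization. Protocol 8.1.2 says that placebo capsules look identical to LC350189 capsules.

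Protocol 8.4.1 has its own formula: total capsules minus those left in the bottle, divided by days in the treatment period, the same for every arm.

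**The concern.** To apply SAP 7.2.2 to a subject one must know the arm (to choose the divisor) and, in the 100 mg arm, which bottle held active drug (to count B). Neither is known under the blind. The meeting that is to set the compliance rules therefore cannot see the SAP's own compliance measure, by subject or as a distribution. The SAP gives no blinded version. It does not say who would compute compliance for the meeting, or whether PPS membership is derived before or after the codes are opened.

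There is a second problem, which remains with the codes open. SAP 7.2.2 defines the measure in several places, and the definitions do not agree. A programmer following one or another would report 100% or 200% for the same fully compliant subject.

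At stake are the reported compliance figures and the claim that the PPS was defined under the blind by a rule fixed in advance.

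**Working it through.** The documents state no compliance result to reproduce, so the check applies each written formula to a fully compliant subject.

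**Inputs**
- Two capsules a day, one from each of two bottles (Protocol 8.4); 35 capsules per bottle (SAP 7.2.1).
- Dosing for 83 days (SAP 3.1), with no dose counted on Day 84 (footnote in SAP 7.2.2).
- C by period with visits on schedule (SAP 7.2.2): 28 − 1 = 27, 56 − 28 = 28 and 84 − 56 = 28. Overall: 84 − 1 = 83.
- 38 subjects per arm, 152 in total.

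**1. Arm formulas, with B as defined in the sentence below the formula table**
- 100 mg, active bottle only: B = 83, B/C = 83/83 = 100%.
- 50 mg, 200 mg and placebo, both bottles: B = 166, (166/2)/83 = 100%.

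Read this way, with the code known, the metric works in all four arms.

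**2. Period rows of the second table in SAP 7.2.2**

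Here B is a sum of 35 minus capsules left, taken over each bottle. For Visit 4 to Visit 6 a full complier returns 8 capsules per bottle, so B = (35 − 8) × 2 = 54.
- 50 mg, 200 mg and placebo: (54/2)/27 = 100%.
- 100 mg, read literally: 54/27 = 200%. The two later periods give 56/28 = 200%.
- The Overall row goes back to non-placebo capsules, so the same 100 mg subject scores 83/83 = 100%.

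**3. Overall sentence closing the part on subjects randomized before version 5.0**

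This defines overall compliance as (sum of B)/(sum of C), without a division by 2.
- 50 mg, 200 mg and placebo: 166/83 = 200%.
- 100 mg: 83/83 = 100%.

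**4. Protocol 8.4.1**

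This also has no division by 2. If both bottles are counted, every arm scores 166/83 = 200%. The same section describes intake below 80% or above 120% as noncompliant, so the formula and the two-capsule regimen need to be reconciled.

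**5. One treatment-blind formula**

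Take all capsules used from the two LC350189/placebo bottles, divide by 2, then by C.
- Full complier, every arm: (166/2)/83 = 100%; in the first period (54/2)/27 = 100%.
- In the 50 mg, 200 mg and placebo arms it always equals the value in step 1.
- In the 100 mg arm (38/152 = 25% of subjects) it equals (active % + placebo %)/2. It differs from active-capsule compliance only when the bottles are used unequally, by |active % − placebo %|/2.
- Active 70%, placebo 100%: 85% against 70%. Active 100%, placebo 70%: 85% against 100%.

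**The case against.** The strongest reply is that nothing forces a breach of the blind. A reader might infer that PPS membership must be decided either with the codes open or on wrong compliance values. The documents do not support that. SAP 4.4.4 assigns rules to the meeting, not a named list of exclusions, and rules set blind can be applied by program after unblinding. The algorithm is among the items left to the meeting, so it could adopt an arm-neutral count. SAP 4.2 also allows for people whose tasks require unblinding. All of this stands. What remains is that the SAP chooses none of these routes, and that 4.4.4 leaves open what 7.2.2 has already fixed.

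A reader might also infer that many compliant subjects would be lost from the PPS, by taking 80% to 120% as the limits and supposing that dummy labels pick the divisor. That is not supported either. The band in Protocol 8.4.1 concerns possible withdrawal, and no PPS cutoff has been set. Anyone able to count active capsules already knows the arm. The completer sentence in 4.4.4, read literally, keeps such subjects in whatever their score.

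Nor are sites obstructed by the SAP formula: Protocol 8.4.1 gives them a total-capsule formula that needs no code.

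On the period rows, the general definition of B in the sentence above that table can fairly be read as covering them, which would give 100% on 100 mg. So the 200% there follows from the literal wording, not from a clear intention. The missing division by 2 in the later Overall sentence has no such explanation in the text.

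Finally, the PPS is supportive and the Full Analysis Set is primary. That is right, and it limits the weight of the point.

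**Conclusion.** The point holds in a limited form. SAP 7.2.2 has two arm-dependent formula forms, and neither can be applied to an individual subject under the blind. SAP 4.4.4 assigns the compliance algorithm and cutoffs to a blinded meeting without saying how compliance will be made available to it, and treats as undecided an algorithm stated elsewhere in the same document.

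The written definitions also disagree by a factor of two for a fully compliant subject:
- on 100 mg, between the period rows (literal reading) and the Overall row;
- on 50 mg, 200 mg and placebo, between the arm formula and the Overall sentence for subjects randomized before version 5.0.

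These figures assume visits on the scheduled days and 83 days of full dosing from both bottles. They show what the formulas return and do not predict how many subjects would be excluded, since no PPS cutoff is stated. The effect is limited to reported compliance and the supportive PPS. The primary analysis on the Full Analysis Set is untouched.

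The unassigned-dose rule raises the same blinding question (SAP 7.2.4: "Subjects who ever took unassigned dose will be excluded from PPS", unless taken for the entire treatment duration), because the dose taken is also hidden under the blind. The conclusion here does not rest on it.

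**What to change.** In SAP 7.2.2, use one formula for every arm, by period and overall: (capsules dispensed minus capsules returned over the two LC350189/placebo bottles)/2/C. Use the same two bottles for subjects randomized before version 5.0. Use this index at the blinded meeting and for the PPS cutoffs. Show the active-capsule version after unblinding as a supportive listing.

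The text then needs four corrections:
- make the period-row definition of B agree with the Overall row;
- put the division by 2 into the Overall sentence for subjects randomized before version 5.0;
- reconcile 4.4.4 with 7.2.2, so that the algorithm is either fixed or open, and say whether the completer sentence overrides a compliance exclusion;
- reconcile the formula in Protocol 8.4.1 with two capsules daily.

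The cost is SAP and protocol wording and a simpler derivation. The real loss is in the 100 mg arm: when the two bottles are used unequally, the blinded index departs from active-drug intake. A subject at 70% on active and 100% on placebo shows 85%, which can mask under-exposure that the active count reveals. The supportive listing is there to show such cases. For subjects already randomized to febuxostat, the blinded index would not count the febuxostat bottle, so their active-drug compliance would appear only in that listing. Their efficacy data are only to be listed in any case.

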12.2.1.3 Per-Protocol Analysis Set

The Per-Protocol (PP) Analysis Set is defined as all subjects in the FAS that have appropriate exposure to study medication for the 12-week treatment period and without any major protocol deviations that may impact primary efficacy analysis. The set of major protocol deviations and the range of treatment compliance percentage required will be finalized prior to database lock. If a subject withdrew from the study prematurely without Week 12 data to assess the primary and/or key secondary endpoints, he or she may be excluded from the PP Analysis Set.

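### The per-protocol rules in SAP 4.4.4 and 7.2.4 conflict: read literally, one inclusion sentence makes the compliance, major-deviation and wrong-dose exclusions ineffective for completers with a Day 84 sUA result

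*SAP*

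**What the plan says.** SAP 4.4.4 defines the PPS as Full Analysis Set (FAS) subjects who "are compliant with treatment and have appropriate exposure to study medication for the 12-week treatment period" and are "without any major protocol deviations that may impact primary efficacy analysis". The details are deferred: the deviation list, the handling of wrong doses, the compliance algorithm and the "cutoff treatment compliance values for PPS exclusion will be determined during a blinded data review meeting (DRM) prior to DBL". For early withdrawals without Week 12 data the rule is discretionary: "he or she may be excluded from the PPS".

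The next sentence is mandatory and has no qualifier. It says that if a subject finished treatment and "had sUA result within 84 days +/- 5 days, he or she will be included in the PPS".

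The paragraph after it lets a wrong-dose subject into the PPS if the subject stayed on one of the study's pre-defined doses throughout. SAP 7.2.4 states its own rule: "Subjects who ever took unassigned dose will be excluded from PPS, unless the unassigned doses taken were administered for the entire treatment duration".

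Protocol 12.2.1.3 requires "appropriate exposure to study medication for the 12-week treatment period and without any major protocol deviations". It has no sentence that admits completers on the strength of an in-window sUA result. The schedule of assessments sets Visit 8 at Day 84 ±2 days (Protocol Table 2-1, repeated in SAP 14.1). SAP section 12 reports no changes to the protocol's statistical section.

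**The concern.** Some subjects satisfy the inclusion sentence and fail the definition. The SAP then gives two opposite instructions and does not say which prevails. Two programmers could follow the document faithfully and build different sets, although the SAP introduction gives pre-specification as its purpose.

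A per-protocol set is meant to show the effect in subjects who took their assigned treatment as planned. If poor compliance, major deviations and mixed dosing no longer remove completers, the PPS loses most of its value as a check on the FAS result. The sharpest case is mixed dosing. The PPS is analysed by treatment received, but the rule that places a mixed-dose subject under the most frequently taken dose (SAP 7.2.4) is written for the safety tables. For efficacy in the PPS such a subject has no defined arm, in a trial whose primary objective is to find the therapeutic dose.

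**Working it through.** **1. The rules side by side.** Take three completers, each with an sUA result between Day 79 and Day 89 (84 ± 5).

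| Completer | Inclusion sentence, SAP 4.4.4 | Other rule |
|---|---|---|
| Below the compliance cutoff the data review meeting sets | In | Out: definition, SAP 4.4.4 |
| Major deviation affecting the primary analysis | In | Out: definition, SAP 4.4.4 and Protocol 12.2.1.3 |
| Mixed doses during treatment | In | Out: SAP 7.2.4 |

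Such subjects can occur. Protocol 8.4.1 makes withdrawal for persistent non-compliance (below 80% or above 120%) optional, so a non-compliant subject can complete. SAP 7.2.4 itself anticipates unassigned doses.

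The two wrong-dose rules also differ from each other. SAP 7.2.4 exempts anyone who took the unassigned dose for the whole treatment period. SAP 4.4.4 adds that the dose must be one of the pre-defined ones. The 150 mg example in 7.2.4 therefore escapes the 7.2.4 exclusion but does not meet the 4.4.4 allowance.

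**2. The plan's own figures.** Protocol 12.4 and SAP 4.1 use p_t = 0.80, p_c = 0.47, Z_α = 1.96 and Z_β = 0.84:

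n = (1.96 + 0.84)² × (0.80×0.20 + 0.47×0.53) / (0.80 − 0.47)² = 7.84 × 0.4091 / 0.1089 = 29.45, so 30.

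With 20% dropout, 30 / 0.8 = 37.5, so 38 per arm, and 4 × 38 = 152. Power for 0.80 against 0.10 with 30 per arm exceeds 99.9%, as stated. All of these reproduce, and none depends on the PPS. The documents give no planned PPS size.

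**3. How many subjects could be affected.** At the planning dropout, completers number 38 × 0.8 = 30.4 per arm. Let f be the share of completers with a reason for exclusion. The documents give no value for f, so a range is shown. The last column assumes that per-protocol response is 0.80 and that the excludable completers respond at 0.2 to 0.6 (also an assumption). It is calculated as (1 − f) × 0.80 + f × r.

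| f | Kept contrary to the definition, per arm (30.4 f) | PPS per arm under the definition | Rate if all completers are kept |
|---|---|---|---|
| 5% | 1.5 | 28.9 | 0.77–0.79 |
| 10% | 3.0 | 27.4 | 0.74–0.78 |
| 20% | 6.1 | 24.3 | 0.68–0.76 |
| 30% | 9.1 | 21.3 | 0.62–0.74 |

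Even with 21.3 per arm, power for 0.80 against 0.10 stays above 99.9%.

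**4. Effect of one retained subject.** Adding one subject to reach n = 30 moves the rate by (response − rate)/30:

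- At a rate of 0.80, a non-responder moves it 0.80/30 = 2.7 points and a responder 0.20/30 = 0.7 points.
- At the assumed placebo rate of 0.10, a responder moves it 0.90/30 = 3.0 points and a non-responder 0.10/30 = 0.3 points.

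About 3 points is therefore a ceiling, not a typical value.

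**The case against.** A reader might infer that the sentence overrides the other criteria and turns the PPS into a completers set. The documents do not establish that, for four reasons:

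- They state no order of precedence, and the definition and SAP 7.2.4 are just as mandatory.
- The data review meeting is still told to set compliance cutoffs for exclusion, which would have little purpose if every in-window completer were already in.
- The wrong-dose paragraph that follows would be redundant for in-window completers.
- Even on the literal reading the result is not exactly a completers set, because exclusion of early withdrawals without Week 12 data is only discretionary.

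There is also a natural innocent reading. The sentence directly follows the one on missing Week 12 data, so it may only say what counts as Week 12 data, with a tolerance wider than the scheduled ±2 days. The COVID-19 measures in Protocol 9.1.20, which allow out-of-window visits while dosing continues, make that plausible.

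It is also fair to say that the SAP fixes neither a compliance cutoff nor a list of major deviations, so the documents do not settle whether a particular non-compliant subject would be excluded.

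All of this stands against the claim of an override. It does not remove the conflict. The qualifier that the innocent reading needs is absent, and for mixed-dose completers the clash with SAP 7.2.4 does not wait on any decision by the meeting. A blinded meeting can set cutoffs, but it should not have to choose between contradictory mandatory rules.

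**Conclusion.** The point holds as a conflict of rules. On the literal reading, the inclusion sentence makes the compliance, major-deviation and wrong-dose exclusions ineffective for completers with an in-window sUA result. It has no counterpart in Protocol 12.2.1.3 and is not declared in SAP section 12.

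The reach is limited. The PPS is supportive. The primary population is the FAS as randomized, with dropouts counted as non-responders, and sample size and power do not rest on the PPS. What is exposed is the PPS efficacy results and the hypoxanthine/xanthine change-from-baseline summary in SAP 10.3.1, which names only the PPS.

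Under the assumed 5–30% of excludable completers, about 2 to 9 of some 30 per arm would be kept contrary to the definition. That range, and the response rates assumed for those subjects, are illustrations without a source in the documents. The textual conflict does not depend on them. It should be corrected before lock, but it threatens no primary conclusion.

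**What to change.** Before database lock, replace the inclusion sentence in SAP 4.4.4 with:

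> A subject who meets all other PPS criteria will not be excluded solely because the Day 84 sUA sample falls outside ±2 days but within ±5 days; an in-window result does not override exclusions for compliance, major protocol deviations or unassigned dose (Section 7.2.4).

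Then:

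- Leave the existing discretionary rule for subjects without Week 12 data unchanged. Making an in-window result a requirement for entry would turn that discretion into mandatory exclusion, contrary to Protocol 12.2.1.3. It would also drop completers whose late or early visits the COVID-19 measures allow.
- State one wrong-dose rule for the PPS and use it in both 4.4.4 and 7.2.4.
- Declare the wider window in SAP section 12.

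The cost is a few lines of SAP text. The downside is a slightly smaller PPS than under the literal sentence: about 29 per arm at f = 5% and about 21 at f = 30%, against about 30.
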